5.3.2 Exclusion Criteria

All patients (with or without relapse) will be excluded from this study if they meet any of the following criteria:

- Patients with diagnosis of primary progressive MS (PP-MS);
- Patients have any disease other than MS that could better explain his/her signs and symptoms;
- Patients with any comorbidity with diseases that might alter synaptic plasticity (e.g. Parkinson Disease, Alzheimer Disease, Stroke);
- Patients receiving concomitant treatment with drugs that may alter synaptic plasticity (e.g. cannabinoids);
- Patients with history or presence of any unstable medical condition (e.g. tumor or infection, e.g. chronic infection or severe life threatening infection within the last 6 months);
- Patients who have received any corticosteroids therapy within 3 months prior to the screening;
- Patients with any concomitant disease that may require chronic treatment with systemic corticosteroids or immunosuppressive agents during the course of the study;
- Patients who have received any immunosuppressive agents other to corticosteroids, as monotherapy or combination therapy within 3 months prior to the screening visit;
- Patients with history or currently active primary or secondary immunodeficiency;
- Patients with inadequate liver function, defined by alanine aminotransferase (ALT) $> 3 \times$ upper limit of normal (ULN), or alkaline phosphatase (AP) $> 2 \times$ ULN, or total bilirubin $> 2 \times$ ULN if associated with any elevation of ALT or AP;
- Patients with inadequate bone marrow reserve, defined as a white blood cell count less than $0.5 \times$ lower limit of normal (LLN);
- Patients with moderate to severe renal impairment;
- Patients unable to complete an MRI (contraindications for MRI include but are not restricted to weight ≥ 140 kg, pacemaker, cochlear implants, presence of foreign substances in the eye,

intracranial vascular clips, surgery within 6 weeks of entry into the study, coronary stent implanted within 8 weeks prior to the time of the intended MRI, etc). Patients with contraindication to Gd can be enrolled into the study but cannot receive Gd contrast dyes during their MRI scans;

- Patients with contraindication to gadolinium (Gd) can be enrolled into the study but cannot receive Gd contrast dyes during their MRI scans;
- Patients receiving supplements that, in the Investigator's opinion, may affect the evaluation of fatigue;
- Patients with any known contraindications or hypersensitivity to D-asp or any excipient;
- Patients with any other significant disease that in the Investigator's opinion would impede study assessments or endanger the patient.
- Female patients with positive pregnancy test at baseline or patients with active project of pregnancy during the study;
- Patients with legal incapacity or limited legal capacity;
- Patients have participated in any other investigational study within 8 weeks before the screening visit.

5.4 Criteria for Initiation of Study Treatment

Patients that fulfil all of the inclusion criteria and none of the exclusion criteria at Screening (Visit -1, Day -5/-3) will enter the 3-5 days of screening phase. All inclusion and exclusion criteria will be checked again at Baseline (Visit 0, Day 0-Week 0). All patients still eligible at the Baseline visit (Visit 0, Day 0-Week 0) will be randomised to receive treatment with D-asp or matched placebo.

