5.3.1 Inclusion Criteria

All patients (with or without relapse) must fulfil all of the following criteria to be eligible for this study:

- Males and females between 18 and 55 years of age;
- Patients with RRMS, according to the revised McDonald Criteria (2010) (Polman et al, 2011);
- Patients with an expanded disability status scale (EDSS) score between 0 and 3 before screening visit (Kurtzke, 1983) and before relapse (if applicable);
- Patients receiving treatment with IFN beta 1a 44 mcg TIW for at least 6 months but for no more than 10 years before the screening visit;
- Female patients must be neither pregnant nor breastfeeding and must lack childbearing potential as defined by either:
 - Postmenopausal or surgically sterile, or
 - Using a highly effective method of contraception for the duration of the study.

Furthermore, female patients must not have been pregnant from at least three months prior to enter in the study;

- Patients willing and able to comply with the protocol for the total duration of the study;
- Patients able to understand the purposes and the risks of the study;

- Patients have signed the appropriate written informed consent form, approved by the Independent Ethics Committee (IEC), prior to the performance of any study activities.

Patients with relapse must fulfil the additional following criterion to be eligible for this study:

- Deterioration of at least one step in a relevant functional system scale (FSS) (Visual, Brainstem, Pyramidal, Cerebellar and Ambulation score) or an increase in EDSS of 1 point or more compatible, according to physician's judgment, with the therapy prosecution;
- Relapse started within maximum 5 days before the inclusion in the study.

Patients without relapse must fulfil the additional following criterion to be eligible for this study:

- Clinically stable RR-MS.

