D-asp at the dose of 2660mg or placebo will be administered once a day for 24 weeks in the form of identical oral solution preparations. The IP (D-asp or placebo) should be administered preferably after the meal.

The content of a sachet should be cleared out in an empty glass. Then approximately 100 ml of still water should be added and the product should be mixed until the effervescence is ended. The product should be administered immediately after the preparation.

Placebo will be undistinguishable from D-asp in terms of packaging, size, colour, weight, appearance, taste and mode of administration.

6.3

Assignment to Treatment Groups

Patients presenting with a relapse and meeting the eligibility criteria during a screening period of 3-5 days will be randomised in a 1:1 ratio via e-CRF to:

- D-asp,
- Placebo.

It is planned to randomise 80 patients with relapse. Randomisation will be stratified according to age (<30 years vs. \geq 30 years) and site location (Rome+Naples+Pozzilli vs. the other sites).

Patients without a relapse will be recruited only at the Pozzilli site and will be randomised in a 1:1 ratio via e-CRF to:

- D-asp,
- Placebo.

It is planned to randomise 40 patients without a relapse. Randomisation will be stratified according to age (<30 years vs. \geq 30 years)

The randomisation list will be in a balanced block design and will be centralized. In each site, eligible patients will be sequentially assigned to the next study number as they present themselves for the study, starting from the lowest number provided for each centre. If a patient discontinues from the study, the patient number will not be reused, and the patient will not be allowed to re-enter the study.

It will be the responsibility of the Investigator (or designee) to explain, and make sure patients fully understand any appropriate treatment related information.

6.4

Non-investigational Medicinal Products to be Used

Treatment with the IP (D-asp 2660mg once daily or placebo) will be administered as add-on to conventional therapies (IFN beta-1a 44mcg TIW for patients without relapse and IFN beta-1a 44mcg TIW plus methylprednisolone i.v. for patients with relapse, for 5 consecutive days at 1000mg once daily).

The prescription of IFN beta-1a in the individual patients will be totally independent from his/her inclusion in the study.

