- A urine pregnancy test will be performed in female patients to exclude pre-existing pregnancy (is not required if the patient is postmenopausal or surgically sterilized or if a serum pregnancy test was already performed within 7 days before the Baseline visit);
- Administration of the EDSS;
- Administration of the 25-FWT, the 9HPT, the Symbol Digit Modalities Test and the Low Contrast Letter visual Acuity Test;
- Administration of the MFIS and of the Fatigue Severity Scale;
- Patients satisfying all eligibility criteria will be randomised to the assigned treatment group;
- IP will be dispensed to patients with directions for use. Patients will be reminded to return the unused IP at the next visit;
- Neurophysiological assessments (LTP and recruitment curve) will be performed in patients without relapse enrolled at the centre of the PPD [REDACTED]
- A blood sample will be collected (before receiving corticosteroids) for immune-phenotype and immunometabolic analysis in patients enrolled in the centres of Rome, Naples and Pozzilli;
- A brain MRI will be performed whenever possible, according to local clinical practice;
- Adverse events occurred from the previous visit and/or during this visit will be recorded;

Once all procedures and assessments for this visit are completed, an appointment for the next visit will be made.

Visit 1 (Week 8)

The following procedures and assessments will be performed at this Visit:

- Any change in concomitant medications will be recorded;
- Physical examination including height, weight, BMI, waist circumference, blood pressure, heart rate;
- Neurological examination;
- A blood sample will be collected for haematology and blood chemistry tests, according to local clinical practice;
- A urine sample will be collected for routine urinalysis, according to local clinical practice;
- Administration of the EDSS;
- Administration of the 25-FWT, the 9HPT, the Symbol Digit Modalities Test and the Low Contrast Letter visual Acuity Test;
- Administration of the MFIS and of the Fatigue Severity Scale;
- Neurophysiological assessments (LTP and recruitment curve) will be performed in patients without relapse enrolled at the centre of the PPD
- A blood sample will be collected for immune-phenotype and immunometabolic analysis in patients enrolled in the centres of Rome, Naples and Pozzilli;
- IP will be returned by patients and compliance to therapy will be evaluated.

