8.1 Sample Size

The primary study endpoint in the part of the study focused on relapsed patients is defined as the proportion of patients who, following a disease relapse associated with a worsening in their MS-related disability, return to baseline status within 8 weeks. Disability will be assessed through the Functional Systems Scores of the EDSS (Visual, Brainstem, Pyramidal, Cerebellar, Sensory, Bowel/Bladder and Ambulation score).

Available data from observational studies (Hirst et al, 2012) indicate that approximately 50% of the patients return to baseline EDSS within 2 months with standard treatments. Based on the fact that usually, in clinical studies where a rigid intention-to-treat (ITT) approach is used, a lower rate of responses/recoveries is observed as compared to observational studies, the expected rate of recovery at 2 months in the control group is set at 40%. With 40 patients per arm the study will be able to detect with 80% power, at the 0.05 alpha level (1-sided), an increase in the proportion of recovery at 2-months from 40% to 70%. The 1-sided significance level is justified by the exploratory nature of this study, aimed at generating study hypotheses to be tested in subsequent studies.

A total of 120 patients will be randomised to include the 40 RR-MS patients without relapses. This subgroup of patients without relapse has been included to assess whether D-Aspartate enhances LTP induction, by means of TMS

Refer to Section 6.3 for procedures of randomisation.

Eligible patients at the end of the screening period will be randomised in a 1:1 ratio to D-asp or placebo. Randomisation will be stratified according to age (<30 years vs. \geq 30 years) and site location (Rome+Naples+ Pozzilli vs. the other sites).

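### In the cohort without relapse, nothing TMS-specific has to be shown before randomisation, so some of the 20 places per arm can go to patients who give no LTP value or no baseline LTP

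*Combined protocol and SAP*

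**What the plan says.** Section 8.1 gives the reason for the cohort: "This subgroup of patients without relapse has been included to assess whether D-Aspartate enhances LTP induction, by means of TMS". Section 6.3 gives its size, "It is planned to randomise 40 patients without a relapse", and its allocation: "Patients without a relapse will be recruited only at the Pozzilli site and will be randomised in a 1:1 ratio via e-CRF to" D-asp or placebo. That makes 20 per arm, a figure the protocol does not print.

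Section 5.4 makes continued eligibility the only condition for randomisation: "All patients still eligible at the Baseline visit (Visit 0, Day 0-Week 0) will be randomised to receive treatment with D-asp or matched placebo". The only inclusion criterion specific to these patients (section 5.3.1) is "Clinically stable RR-MS". Section 5.3.2 has an exclusion that begins "Patients unable to complete an MRI (contraindications for MRI include but are not restricted to weight" and applies to everyone, although MRI is done only where local practice allows. There is no counterpart for TMS, which is scheduled for this cohort at baseline and at weeks 8, 12 and 24 (section 7.7).

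TMS is not done at screening. In the Visit 0 list of section 7.1, "Patients satisfying all eligibility criteria will be randomised to the assigned treatment group" comes first, then "IP will be dispensed to patients with directions for use", then the neurophysiological assessments. Table 1 also puts the randomisation row above the TMS row, but puts IP dispensing below TMS. In the Visit 0 list, the only sampling or recording given an explicit order is the immunology blood, which must precede corticosteroids.

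**The concern.** An LTP value needs recordable MEPs in the right FDI muscle and a completed iTBS session, because section 7.7 expresses the post-iTBS amplitude relative to the pre-iTBS mean. Neither condition has to be known when the patient is randomised. A patient for whom TMS proves impossible has by then taken one of the 40 places and belongs to the ITT set (section 8.3). The protocol has no replacement rule, and a discontinued patient's number is not reused (section 6.3). Nor does it give a missing-data rule for LTP.

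At stake is the precision of the comparison for which the cohort was added. The cohort is small and will probably lose patients later as well, since section 5.5.1 takes those who relapse during treatment off IP. Losses that could be found before randomisation are better found there. The unstated order at Visit 0 raises a second, smaller matter: no text places the baseline recording before the first sachet.

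**Working it through.** **Step 1: the plan's own figure.** The only power statement (section 8.1) concerns the relapse cohort: 40% against 70%, one-sided 0.05, 80% power, 40 per arm. With mean proportion 0.55:

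n' = [1.645 × √(2 × 0.55 × 0.45) + 0.842 × √(0.24 + 0.21)]² / 0.30² = 32.9, so 33 uncorrected.

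With continuity correction: n = (32.9/4) × [1 + √(1 + 4/(32.9 × 0.30))]² = 39.3, so 40.

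The stated 40 per arm reproduces and is unaffected by this point. The protocol states no effect size, SD or power for LTP.

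**Step 2: what is known about TMS before randomisation.**

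| Source | What it covers | What it leaves open |
|---|---|---|
| 5.3.1, ability to comply | General willingness and capacity | Judged without a TMS attempt |
| 5.3.2, other disease impeding assessments | Known illness, in the investigator's opinion | An unrecordable MEP found only on testing |
| 5.3.2, MRI contraindications | Pacemaker, cochlear implants, intracranial clips | Tolerance of iTBS; MEP recordability |
| 7.1 and 9.2, separate TMS consent | Willingness of those who take part | Technical feasibility |
| 5.4 | All still-eligible patients are randomised | No condition on the TMS session |

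The gap does not depend on the order of procedures within Visit 0. Even if TMS were done first, no result of it is a condition of randomisation.

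**Step 3: what a failure costs.** LTP is normalised within each session. A failure at Visit 0 alone therefore does not prevent values at weeks 8, 12 and 24. It removes the baseline and leaves an incomplete series for the repeated-measures ANOVA of section 8.4.3, which in its standard form uses complete series. A patient who can never complete TMS gives no LTP value.

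**Step 4: size.** Inputs:
- 20 per arm (40 at 1:1, section 6.3).
- Two-sided 5%, the default in section 8.4.1.
- A non-evaluable share of 5% to 20%, assumed.
- A true effect of 0.9 SD, assumed; it is close to what 20 per arm detects with 80% power.

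The calculation is a two-sample t-test at one time point, with losses split evenly and each counted as complete. Power comes from the noncentral t distribution with noncentrality 0.9 × √(n/2) and 2n − 2 degrees of freedom. At n = 20 the noncentrality is 0.9 × √10 = 2.85 with 38 degrees of freedom.

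| Assumed non-evaluable | Places lost of 40 | n per arm | Power at 0.9 SD | Difference detectable with 80% power |
|---|---|---|---|---|
| 0% | 0 | 20 | 79% | 0.91 SD |
| 5% | 2 | 19 | 77% | 0.93 SD |
| 10% | 4 | 18 | 75% | 0.96 SD |
| 15% | 6 | 17 | 72% | 0.99 SD |
| 20% | 8 | 16 | 69% | 1.02 SD |

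Each patient lost per arm costs 2 to 3 points of power.

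**The case against.** The strongest reply is that this is a modest gap in a secondary endpoint of a pilot. Much of it stands.

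- **Order at Visit 0.** A reader might infer that IP is dispensed, or even taken, before baseline TMS, so that baseline LTP is not a pre-treatment value. The documents do not support this. The section 7.1 list is not said to be chronological and cannot be: it confirms eligibility before the urine pregnancy test, whose positive result is an exclusion. Table 1 puts dispensing after TMS, and dispensing is not dosing. What remains is that the order is unspecified and the two lists differ on dispensing.
- **Existing safeguards.** It would be too strong to say that nothing guards against TMS failure. The general criteria, the MRI contraindications and the separate consent cover part of it. What is missing is a TMS-specific criterion.
- **Contribution of patients who fail.** A reader might suppose that a failed baseline session leaves a patient with nothing to offer. Within-session normalisation allows later LTP values, and clinical, fatigue, immunological and safety data are still collected.
- **Bias.** Losses after randomisation might suggest a biased comparison. A technical failure before any dose, under blinding, cannot be caused by treatment. No directional bias is shown.
- **Magnitude.** The failure rate and the effect size are assumptions. Treating each failure as a total loss at one time point overstates the cost where only Visit 0 fails. At 5% to 10% the loss is about 2 to 5 points of power.

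The reply does not remove the central point: none of the safeguards tests whether an MEP can be recorded or an iTBS session completed.

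**Conclusion.** The point holds as a cheap improvement. For the 40 patients without relapse, the protocol requires neither a TMS-specific criterion nor a completed baseline TMS session before randomisation, and it does not place that session before the first IP dose. Places in a 20-per-arm comparison can therefore go to patients who give no LTP value, or no baseline for it.

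The consequence is lost precision on one secondary endpoint. Power at 0.9 SD falls from 79% to between 77% and 69% if 5% to 20% are non-evaluable. That range, the 0.9 SD effect and the single-time-point t-test are illustrative choices, not figures from the plan. No stated figure is wrong, and the primary analysis in the relapse cohort is unaffected.

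**What to change.** For patients without relapse only:

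1. In section 5.4, Table 1 and section 7.1 (Visit 0), state that the baseline TMS session takes place before randomisation and before the first IP dose.
2. Randomise only patients with a recordable pre-iTBS MEP in the right FDI who completed the session. Neither the post-iTBS amplitude nor the LTP response may be a criterion, because that would select on the outcome.
3. In section 5.3.2, add inability to complete TMS as an exclusion, in the form of the existing MRI criterion.

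Patients who fail then become screen failures instead of losses after randomisation. Later losses, such as withdrawal from IP on relapse, are not addressed by this change.

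The session is already planned at this visit and at this one site, so no visit or procedure is added. The cost is extra screen failures at Pozzilli. Randomising 40 evaluable patients means bringing 40/(1 − f) to Visit 0. That is 43, 45, 48 or 50 at assumed failure rates f of 5%, 10%, 15% or 20%, so 3 to 10 more patients. Without the check, the same 43 to 50 would have to be randomised to end with 40 evaluable.

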5.5 Criteria for Subject Withdrawal

5.5.1 Withdrawal from Study Therapy

A patient must be withdrawn from IP if any of the following occur:

- Patient withdraws consent;
- Patient is lost to follow up;
- Participation in another clinical study;
- Occurrence of an exclusion criterion which is clinically relevant and affects the patient's safety, if discontinuation is considered necessary by the Investigator and/or Sponsor;
- Therapeutic failure requiring urgent additional drug;
- Any events that unacceptably endanger the safety of the patient;
- Occurrence of adverse events, if discontinuation of study drug is desired or considered necessary by the Investigator and/or the patient;
- Occurrence of pregnancy;

- Serious intercurrent illness or significant worsening of intercurrent illness;
- MS-related neurological events requiring steroid treatment (in this case, an ET visit will be conducted, during which a blood sample will be taken before the start of the steroid treatment);
- Patients without relapse at entry in the study that will relapse during the 24-week treatment phase.

If a patient prematurely withdraws from the IP at any time during the study, he/she will undergo all assessments requested at the ET visit ([Section 7.1](#)) as soon as possible after his/her last injection. In any case, the appropriate electronic Case Report Form (e-CRF) section including the reason(s) for withdrawal from the IP must be completed.

5.5.2 Withdrawal from the Study

Patients may withdraw from the study at any time without giving a reason.

Patient must be withdrawn from the study if a patient withdraws the informed consent. Withdrawal of consent will be considered as a withdrawal from the study.

Patient must be also withdrawn from the study if he/she participates in another clinical study.

If a patient has failed to attend scheduled study assessments, the Investigator must determine the reasons and the circumstances as completely and accurately as possible.

If a patient fails to return for assessments, attempts should be made to contact the patient to determine whether or not the reason for not returning is an adverse event. Likewise if a patient declares his/her wish to discontinue the study, e.g., for personal reasons, an attempt should be made to establish whether or not the true reason is an adverse event (bearing in mind the patient is not obliged to state his/her reasons).

If a patient prematurely withdraws from the study at any time, he/she will undergo all assessments requested at the ET visit ([Section 7.1](#)) as soon as possible after his/her last injection. In any case, the appropriate e-CRF section including the reason(s) for withdrawal from the study must be completed.

The patient who has withdrawn early will receive other appropriate treatment, in accordance with the study site's standard of care and generally accepted medical practice and depending on the patient's individual medical needs.

